#### 7. POWER ANALYSIS

The primary objective of this trial is to detect a difference in the duration of sleep between delirious and nondelirious patients. Assuming a delirium event rate of 15%, a type I error of 0.05, power of 0.90 and a SD of 60 minutes, n = 13 patients with delirium and 78 patients without delirium will enable us to detect an absolute total sleep time difference of 60 minutes between both groups (i.e., 360 minutes versus 300 minutes). Therefore, anticipating a dropout rate of approximately 10%, we aim to recruit 100 subjects.

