#### Treatment Assignment and Randomization: Not applicable.

#### 5. Study Design

Pre-operative Visit: We will obtain a written consent prior to conducting the Long-CAM, PSQI, Patient Health Questionnaire (PHQ-9), Trust in Physician Scale (TPS) and the abbreviated Montreal cognitive assessment. Next, we will place a portable PSG device at approximately 7 pm to record neurophysiological data using the Compumedics Portable PSG monitoring device. Due to clinical care concerns, patient acuity, patient unavailability and several other unforeseen factors, PSG may not be placed on all study subjects. A minimum of the following electrodes will be placed for sleep staging: Two central channels (C3 and C4), two electrooculogram channels to capture lateral eye movements, and two reference channels over the left and right mastoids.

Post-operative Day 0: PSG electrodes will be removed at approximately 6am. Additionally, we will obtain approximately 13ml of blood to be processed into mRNA to understand the association between peri-operative circadian cycle disruption of four circadian clock genes (Bmal1, Clock, Per1 and Per2) and POD. The PI will ensure that appropriate privacy and de-identification procedures are in place for the collection and storage of blood. All MGH ORs are equipped with a four-channel frontal EEG device (Sedline, Masimo, Irvine, CA). Thus, we will collect intraoperative routine EEG data that is recorded as part of routine anesthetic management. Due to clinical care concerns, patient acuity, Sedline electrode unavailability and several other unforeseen factors, blood and Sedline EEG data may not be obtained on all study subjects.

Post-operative Days 1-3: On post-operative day 1, we will obtain approximately 13ml of blood as a post-surgical measure of mRNA levels to understand the association between peri-operative circadian cycle disruption of four

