## 6. DATA ANALYSIS PLAN

Hypothesis tests will be performed using a two-sided significance level (type I error) of  $\alpha$ =0.05. Aim 1 (Hypotheses 1 and 2) outcome will be evaluated using binominal regression models with adaptive elastic net penalty to examine the association between total sleep time and POD. Patient characteristics of interest (i.e. age, gender, baseline cognitive score, pain, depression symptom score, frailty index, Charlson comorbidity index) will be included into this regression model. Because missing data rarely occur entirely at random, we will assess associations between patient characteristics with respect to missing data. If patients with at least one missing outcome value are different from those with complete outcomes data, we will use multiple imputation to assign values to missing data risk factors and outcomes in regression modeling. Aim 2 (Hypothesis 1) Wilcoxon rank-sum tests with corrections for multiple comparisons will be used to assess differences for each analyte or transcript. In other exploratory analysis, we will assess differences in the EEG (PSG and intraoperative) dynamics of delirious and non-delirious patients. To assess statistical significance for the difference in EEG spectra at each frequency, we will compute the 99% confidence interval of the median difference between groups by using an empirical bootstrap approach. The null hypothesis will be rejected only if the confidence interval of the median difference at each frequency exceeds the significance threshold over a contiguous frequency range  $\geq$  2W. We will also characterize differences in sleep microstructure dynamics (i.e. spindle power, spindle rate, spindle peak frequencies, slow-delta phase- spindle amplitude modulation) between groups using algorithms developed in-house.

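### The 0.90 power in Section 7 belongs to an unadjusted comparison of mean sleep time in 91 patients with PSG, and is not justified for the penalised binomial analysis that Section 6 plans

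*Combined protocol and SAP*

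**What the plan says.** Section 7 gives the primary objective as to "detect a difference in the duration of sleep between delirious and nondelirious patients". It assumes a 0.05 type I error, a 15% delirium rate and means of 360 and 300 minutes, and states "power of 0.90 and a SD of 60 minutes, n = 13 patients with delirium and 78 patients without delirium". The plan is to recruit 100 to allow for about 10% dropout. Covariates and missing PSG are not mentioned.

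Section 6 sets the test level: "Hypothesis tests will be performed using a two-sided significance level (type I error) of" 0.05. For Aim 1 it plans binomial regression with an adaptive elastic net penalty, so POD is the outcome and TST a predictor. Seven patient characteristics enter as well: age, gender, cognitive score, pain, depression score, "frailty index, Charlson comorbidity index) will be included into this regression model". Multiple imputation of risk factors and outcomes is conditional: it is used if patients with a missing outcome differ from those with complete outcomes.

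Section 5 says that, for clinical and practical reasons, "PSG may not be placed on all study subjects". No expected completion rate is given.

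**The concern.** The study's one power figure and its one Aim 1 analysis do not describe the same test. Section 7 powers a difference in mean sleep time between two groups. Section 6 models the odds of delirium with TST as one of eight predictors (13/8, about 1.6 events per predictor) and shrinks the coefficients. Nothing in Section 6 estimates the difference in minutes that Section 7 makes the primary objective: the Wilcoxon tests are for the Aim 2 transcripts, and the bootstrap intervals are for EEG spectra. Nor does Section 6 say how a test at the 0.05 level is to be obtained from the penalised fit.

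The calculation also assumes a measured TST in all 91 patients, while Section 5 expects that some will have none.

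What is at stake is how a null result is read. A non-significant TST term from the planned model, in those patients who had PSG, would be set against a 90% power claim that was never computed for that analysis.

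**Working it through.** **Inputs.** From Section 7: difference 60 minutes, SD 60, groups of 13 and 78, event rate 15%, dropout about 10%, 100 recruited. From Section 6: two-sided 0.05, seven covariates. From Section 5: incomplete PSG, no rate. The documents give neither a PSG completion rate nor any covariate relation to sleep or delirium. Every value used for these below is an assumption.

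**1. The plan's own figure.** Standardised difference d = 60/60 = 1. Noncentrality = d / sqrt(1/13 + 1/78) = 3.338, with 13 + 78 − 2 = 89 degrees of freedom and critical value 1.987. Two-sided t-test power from the noncentral t distribution is **0.910**. The normal approximation gives Φ(3.338 − 1.960) = 0.916. The stated 0.90 is thus reproduced as an unadjusted comparison with TST on all 91.

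**2. Slack after dropout.** 100 × 0.90 = 90 patients, against the 91 assumed. The difference of one is trivial given an approximate dropout rate, but it leaves nothing for further loss. The number of delirium cases will also vary. Averaging the t-test power over a Binomial(N, 0.15) number of cases gives 0.902 at N = 91 and 0.899 at N = 90.

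**3. PSG missing beyond the 10%.** Same unadjusted test, averaged over Binomial(N, 0.15), starting from 90:

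| Assumed further loss | Evaluable N | Power |
|---|---|---|
| 0% | 90 | 0.899 |
| 10% | 81 | 0.866 |
| 20% | 72 | 0.824 |
| 30% | 63 | 0.770 |

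**4. Covariate adjustment.** The penalised model's power cannot be computed, because no test is specified for it. As a stand-in, unpenalised logistic regression of POD on TST and seven covariates was simulated at 13 v 78, with a marginal difference of 60 minutes and SD 60. Shift means how much higher each covariate is in delirious patients. R² is the share of TST variance that the covariates explain jointly.

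| Assumed covariate relations | Power, Wald | Power, likelihood ratio |
|---|---|---|
| Unrelated to sleep and POD | 0.88 | 0.90 |
| R² 0.2, unrelated to POD | 0.94 | 0.95 |
| Shift 0.2 SD, R² 0.1–0.2, pairwise correlation 0.3 | 0.84–0.87 | 0.87–0.90 |
| Shift 0.2 SD, R² 0.1–0.2, mutually independent | 0.77–0.78 | 0.81 |
| Shift 0.3 SD, R² 0.1–0.2, mutually independent | 0.58–0.67 | 0.63–0.71 |

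The results lie on both sides of 0.90. The low ones arise when all seven covariates are independent and shifted in the same direction, so that their confounding accumulates.

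**The case against.** The strongest reply is that no shortfall has been shown. Section 7's arithmetic is sound. Covariates that predict sleep but not delirium raise power, and correlated covariates cost much less than independent ones. The 10% allowance may have been meant to include missing PSG, and Section 6 plans imputation of missing risk factors, which could recover part of the loss.

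Most of this stands. A reader might infer that the study does not have the power it states, or that adjusting for seven covariates must reduce it. The documents support neither inference, because they give no covariate relations and no PSG completion rate. For the same reason, no single adjusted-power figure should replace the 0.90.

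Two parts of the reply are weaker. Section 7 does not say that the 10% covers PSG. The same allowance may also have to absorb withdrawals, patients dropped for intubation beyond 24 hours (Section 3) and delirium assessments set to missing after reintubation (Section 5). And imputation depends on a comparison of patients with and without missing outcomes, whereas in the Aim 1 model PSG-derived TST is a predictor, so it is unclear that missing PSG alone would trigger it.

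None of the reply answers the central point: the 0.90 was computed for a test that Section 6 does not contain.

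**Conclusion.** The concern holds in this form. The 0.90 is correct for an unadjusted comparison of mean TST in 91 patients with PSG (0.910) and is not justified for the Section 6 analysis. That mismatch is visible from Sections 6 and 7 alone and needs no assumption.

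The size of any loss does depend on assumptions. For missing PSG beyond the dropout allowance, unadjusted power is about 0.87, 0.82 and 0.77 at 81, 72 and 63 evaluable patients. For adjustment, even the direction is not determined.

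This should be corrected, since it concerns the stated primary objective and the correction is cheap.

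**What to change.** 1. **Section 6.** Name as the primary test the comparison that Section 7 powers: the difference in TST between patients with and without POD, in minutes with a 95% CI, unadjusted. Follow it with a covariate-adjusted estimate of the same difference, for example from linear regression of TST on POD status and the listed characteristics. Keep the penalised binomial model as a supporting analysis.
2. **Section 7.** Say that the 0.90 refers to that unadjusted comparison in 91 patients with both PSG and Long-CAM data. State the expected PSG completion rate and whether the 10% covers missing PSG. Give the unadjusted power at smaller evaluable numbers, such as 81, 72 and 63. Do not print adjusted-power figures that rest on an assumed R².

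**Cost.** Protocol wording only; no extra patients or data. The stated power becomes slightly less favourable. An unadjusted primary result in an observational study is open to confounding, so the adjusted estimate must always be reported beside it.

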#### 8. RISK AND DISCOMFORT

**PSG risks**: The risks associated with PSG electrodes are redness, irritation at placement site, unpleasant odor from glue, and annoyance from having electrodes attached to the body.

**Questionnaire risks:** Minimal risks associated with completing questionnaires are subject fatigue and the possibility of minor psychological distress associated with answering sensitive questions regarding psychological functioning.

**Data risks:** Procedures are in place to reduce the likelihood of a breach of confidentiality including the deidentification of data and storage of data only on partners approved devices/portals. However, there is a small risk that people outside of this study may be exposed to information about study subjects.

#### 9. POTENTIAL BENEFITS

Subjects will have no direct benefit from taking part in this study. Findings from these studies will help advance our understanding of the neurobiology of delirium. We envision that in the future the information obtained from the proposed research will enhance the diagnosis and management of POD.

### 10. MONITORING AND QUALITY ASSURANCE

Because this study is a physiological study of sleep neurophysiology, as opposed to a clinical trial, the principal investigator and co-investigators will be responsible for monitoring and quality assurance of the study. In conjunction with the research assistants, weekly meetings will be held and documented. Current subjects in the study will be discussed at each meeting, and charts will be reviewed for completeness. The team will evaluate the progress of the study, verify that the rights and well-being of the subjects are protected, verify that the reported study data are accurate, complete and verifiable from source documents, and the conduct of the study is in compliance with the approved protocol and amendments.

Serious Adverse Events: Expedited review will occur for all events meeting the FDA definition of SAEs – i.e., any fatal event, immediately life-threatening event, permanently or substantially disabling event, event requiring or prolonging inpatient hospitalization, or any congenital anomaly. This also includes any event that a study investigator judges to impose a significant hazard, contraindication, side effect, or precaution. Reporting to the IRB will be done within 24 hours of the SAE.

Study Stopping Rules: If at any time during the course of the study, the PIs or CO-Is judge that risk to subjects outweighs the potential benefits, the PI/CO-Is shall have the discretion and responsibility to recommend that the study be terminated.

AE Reporting Guidelines: Unanticipated problems involving risks to subjects or others including adverse events will be reported to the PHRC in accordance with PHRC unanticipated problems including adverse events reporting guidelines, as well as the RDRC within 5 days.

